**Grant Number: R01DK121316**

## Summary of Changes from Previous Version:

Affected Section(s)	Summary of Revisions Made	Rationale
Protocol 10/16/2019	1) Use of econsent documents 2) Updated 18-year-old consent document 3) Revisions to measures (PAID-T and SCI) to reduce subject burden 4) Additional measures to assess secondary outcomes 5) Revisions to health behavior contract to broaden focus to other diabetes management behaviors 6) Revisions to educational materials to improve readability 7) Revisions to positive affect interview materials to improve clarity 8) Revisions to recruitment script to include more information in the initial approach 9) Study flyer	1) Use of econsent forms to reduce paper and simplify enrollment process. 2) Updated 18 year old consent forms to address request from IRB Analyst. 3-8) Measures: Use of shorter, validated measures to assess outcomes to reduce participant burden. 9) Developed study flyer to aid with recruitment.
Protocol 2/18/2020	We reduced the required score on the diabetes distress measure completed by teens. We added a statement in the verbal consent to be able to collect clinical data (A1C) from participants that consent to screen for the study but do not enroll in the study. We are adding questions to the parental demographics survey to include more information about secondary caregivers. We are removing questions related to diabetes	Based on lower than anticipated numbers screening into the study, we propose to reduce the required score on the diabetes distress measure completed by teens. We are adding a statement in the verbal consent to be able to collect clinical data (A1C) from participants that consent to screen for the study but do not enroll in the study. We are adding questions to the parental demographics survey to include more information about secondary caregivers. We are removing questions related to

	device use that have been deemed superfluous or confusing.	diabetes device use that have been deemed superfluous or confusing.
Protocol 4/20/20	
1) We added questions to the evaluation to ask about the effects of Covid-19 on the participant's experience.
 
2) We added an option to send the participant an at home A1C test if they did not have a diabetes clinic visit.
	
1) In order to understand the impact COVID-19 may have had on diabetes management and mood, we added questions to the teen and parent surveys.
 
2) Due to the increase in telehealth visits, we are not able to obtain point-of-care A1C values from all participants. By sending at-home A1C test kits, we will reduce missing data.

Non-Compliance 11/2/2020	8 participants (4 dyads) were given the incorrect compensation due to incorrect record keeping of Amazon gift card serial numbers. Gift cards worth \$20 were incorrectly recorded by study personnel as worth \$30. Therefore, \$20 compensation was given to 4 dyads instead of the sufficient amount of \$30. The study coordinator at Children's National contacted each affected participant and sent the additional \$10 gift cards once the error was detected.	
Protocol 11/2/2020	Participants who use/have used a continuous glucose monitor (CGM) are given the option to participate in an ancillary study to take part in qualitative interviews about CGM use and reasons for starting and stopping use.	This ancillary study will use qualitative interviews to explore the use of CGM in teens.
Protocol 3/23/2021	We created a recruitment video that is used to give information to prospective participants about our study. We have also drafted language for distributing information about our study on Research Match and the Vanderbilt Research Notifications Distribution list to expand our recruitment efforts.	Additional recruitment efforts to boost enrollment.
Non-Compliance/ Continuing Review 5/17/2021	Many participants were recruited and enrolled through remote method due to Covid-19 restrictions. The HRPP allowed this change without prior approval due to extenuating circumstances. This protocol deviation detailed the covid-related changes we made.	Covid changes in this protocol deviation included the following: Rather than approaching patients in clinic, we used Epic to track which patients were attending appointments through telehealth and called them to recruit for the study. Eligibility surveys were sent through email provided by the participant at the time of the call. – Rather than enrolling participant in the clinic, we enacted the same study protocols over zoom and sent study surveys through email.
Measures 8/26/2021	We added questions to the parental COVID-19 supplemental measure. We are asking participants if any adults (18+) and children (12-17) have been vaccinated in their household. Also, we are asking if their child has seen their	To remain current on how COVID-19 is affecting study participants, we added additional questions to our COVID-19 survey measure related to COVID-19 vaccination status and the use of telehealth clinic visits. Many COVID-19 restrictions currently in place (locally and

	
diabetes provider via telehealth visit since this could impact their quality of care and one of our specific study aims (glycemic control). These changes were only applied to the parent surveys.
 
domestically) are dependent on vaccination status, so these questions will help us to interpret findings related to the effects of COVID-19 on diabetes management and mood.

--	---

## STATEMENT OF COMPLIANCE

1. The trial will be carried out in accordance with International Council on Harmonisation Good Clinical Practice (ICH GCP) and the following:
  - o United States (US) Code of Federal Regulations (CFR) applicable to clinical studies (45 CFR Part 46, 21 CFR Part 50, 21 CFR Part 56, 21 CFR Part 312, and/or 21 CFR Part 812).

National Institutes of Health (NIH)-funded investigators and clinical trial site staff who are responsible for the conduct, management, or oversight of NIH-funded clinical trials have completed Human Subjects Protection and ICH GCP Training.

## 1 PROTOCOL SUMMARY

### 1.1 SYNOPSIS

Title:	Thrive! Positive Psychology Intervention to Treat Diabetes Distress in Teens with Type 1 Diabetes (T1D)
Grant Number:	R01DK121316
Study Description:	The proposed study will conduct a multi-site, randomized trial to test the effects of a positive psychology intervention aimed at treating diabetes distress and improving glycemic outcomes.
Objectives*:	
Primary Endpoint: Glycemic control (HbA1c)
 
Secondary Endpoints:
 

Diabetes Distress

Coping

Positive Affect

Diabetes Management

Quality of Life

Family Conflict

Endpoints*:	
Primary Endpoint: 3 months
 
Secondary Endpoints:
 

6 months

12 months

Study Population:	Adolescents with type 1 diabetes
Phase* or Stage:	Phase 2
Description of Sites/Facilities	Vanderbilt University Medical Center Children's Diabetes Program
Enrolling Participants:	Children's National Medical Center Diabetes Program
Description of Study Intervention/Experimental Manipulation:	The intervention is aimed at inducing positive affect to treat diabetes distress. Adolescents will complete a positive affect interview at baseline. They will receive automated text messages 5 days/week for 8 weeks. Messages will be tailored to include adolescents' responses to the baseline interview, including reminders to engage in gratitude and self-affirmation. Additionally, to induce positive mood they will be texted gift cards codes valued at \$5.00. Further, parents will be asked to provide weekly positive affirmations to their adolescents, focused on non-diabetes strengths. After completing the exit interview participants will be given the option to participate in an interview exploring the role of continuous glucose monitors on diabetes distress and glycemic control.
Study Duration*:	4 years

**Participant Duration:** 12 months

## 1.2 SCHEMA

### 1.3 SCHEDULE OF ACTIVITIES

	Screening	Visit 1	8 Week Intervention Period	Visit 2 (3 months)	Visit 3 (6 months)	Visit 4 (12 months)
Diabetes Distress	x					
Informed Consent/Assent		x				
Outcome Evaluation						
Clinical Data (A1C, BG data)		x		x	x	x
Adolescent Questionnaires		x		x	x	x
Parent Questionnaires		x		x	x	x
Randomization		x				
Health Behavior Contract		x				
Educational Materials		x				
Positive Affect Interview		x				
Automated Text Messages			x			
Exit Interview				x		
Optional CGM interview				x (after visit 2)		
Adverse Events Reporting		x	x	x	x	x

## 2 INTRODUCTION

### 2.1 STUDY RATIONALE

In line with the American Diabetes Association's recommendation to assess for and address diabetes distress, the proposed project will focus on treating adolescents who report at least moderate levels of distress. We will use a positive psychology framework, which emphasizes positive emotions and strengths rather than problems, to treat diabetes distress and improve glycemic outcomes. Positive affect, defined as feelings that reflect pleasurable engagement with the environment (e.g., happy, cheerful, proud), predicts favorable health outcomes, especially in health conditions that have a behavioral component, like diabetes. Backed by empirical evidence from basic behavioral science, the Broaden and Build Theory posits that increased positive affect increases people's ability to use complex coping strategies, such as problem solving and cognitive reframing, which are needed for the complex demands of diabetes management. The current study is based on the premise that, by boosting positive affect in teens with diabetes, we will enhance the use of adaptive coping strategies and reduce diabetes distress, thereby improving glycemic control.

### 2.2 BACKGROUND

Adolescents with type 1 diabetes (T1D) face increased risk for problems with management and deteriorating glycemic control, with only 17% of adolescents meeting the recommended target for hemoglobin A1C. Diabetes distress, or emotional distress related to the burden of living with diabetes, has been strongly associated with poor glycemic control and quality of life in adolescents. Unlike depression, which is episodic in nature, studies in adults with T1D show that diabetes distress remains stable over time without intervention.(4) Further, people who experience even moderate levels of diabetes distress have problems with diabetes management and glycemic control. While psychoeducational interventions have been proven to reduce diabetes distress in adults with T1D, to our knowledge, none have directly targeted diabetes distress in teens, and few have used positive psychology approaches. Thus, there is a need for novel approaches targeting diabetes distress to improve diabetes outcomes in adolescents with T1D.

### 3 OBJECTIVES AND ENDPOINTS

OBJECTIVES	ENDPOINTS	JUSTIFICATION FOR ENDPOINTS	PUTATIVE MECHANISMS OF ACTION
Primary			
Glycemic Control (HbA1c)	Baseline, 3 months, 6 months, 12 months	Corresponding with diabetes clinic visits	
Secondary			
Diabetes Distress, Positive Affect, Coping, Diabetes Management, Quality of Life, Family Conflict, Resilience	Baseline, 3 months, 6 months, 12 months		
Tertiary/Exploratory			
Demographics (adolescent age, sex), use of diabetes devices	Baseline		

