## 5 STUDY POPULATION

### 5.1 INCLUSION CRITERIA

In order to be eligible to participate in this study, an individual must meet all of the following criteria:

- Age 13-17
- Diagnosed with type 1 diabetes for at least 12 months
- Speak and read English
- Report at least moderate diabetes distress on the Problem Areas in Diabetes Scale - Teen version

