### 9.2 SAMPLE SIZE DETERMINATION

**Power Analysis:** We plan to enroll 200 adolescent-parent dyads and conservatively assume a 15% dropout rate, leaving 170 subjects for analysis. Power calculations for the repeated-measures design were conducted using a variety of statistical simulations for each of the outcomes. Inputs into the simulation study, based on preliminary data from 46 subjects measured 3 months apart, were baseline mean, baseline standard deviation, and correlation between baseline and 3-month measurement. Table 3 summarizes the effect sizes that we will have at least 90% power to detect at a 0.05 significance level.

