### 9.3 STATISTICAL ANALYSES

#### 9.3.1 General Approach

Outcomes will be measured at up to four time-points per subject (baseline, 3 months, 6 months, and 12 months), so we will use time, treatment group and the interaction of treatment with time serving as the main explanatory variables. Such a model will allow us to test for any differences between treatment and control groups at 3, 6 or 12 months while accounting for baseline values. While the randomized block design should minimize confounding, we will adjust for age, sex, and race/ethnicity to improve precision. The results from the adjusted and unadjusted models will be compared with respect to their estimates of the treatment effects. We will include a random intercept to account for within-subject correlation arising from taking repeated measurements on the same subject over time. The error structure of the model is assumed to be compound symmetric, and the validity of this assumption will be examined by computing Akaike Information Criteria against other common structures. Subjects will

be included in the analysis if they have an outcome measured at baseline and at least one outcome measured at 3, 6 or 12 months.

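### Conditioning on the Visit 1 A1C and adding one earlier clinic A1C as a covariate would sharpen the primary comparison at small cost

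*Combined protocol and SAP*

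**What the plan says.** Section 3 names A1C as the primary outcome at baseline, 3, 6 and 12 months and justifies the timing as "Corresponding with diabetes clinic visits". The schedule in 1.3 starts A1C collection at Visit 1. The synopsis (1.1) puts the primary endpoint at 3 months, and 9.1 describes the outcome as change in A1C.

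On the model, 9.3.1 says: "Outcomes will be measured at up to four time-points per subject (baseline, 3 months, 6 months, and 12 months". The explanatory variables are time, treatment and their interaction, with age, sex and race/ethnicity added for precision. There is a random intercept, and "The error structure of the model is assumed to be compound symmetric", to be checked against other structures by AIC. The section says the model takes account of baseline, but it specifies neither a baseline covariate nor equal baseline means across arms.

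Entry requires "Diagnosed with type 1 diabetes for at least 12 months" (5.1). Section 5.3 describes pools of 614 and 1100 active patients at the two clinics. No A1C from before Visit 1 is collected for the analysis.

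**The concern.** One A1C is a noisy reading of a teen's usual level. If A1C values share a persistent between-teen component, as a random intercept assumes, an earlier clinic value tells us more about that level than Visit 1 alone. The plan already adjusts for age, sex and race/ethnicity to gain precision. A prior reading of the outcome itself is a natural candidate for the same purpose, and it probably sits in the clinic record already. At stake is the precision of the between-arm contrast, and so the chance of missing a modest effect of an 8-week text intervention.

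**Working it through.** **The plan's own figure.** Section 9.2 states: "We plan to enroll 200 adolescent-parent dyads and conservatively assume a 15% dropout rate, leaving 170 subjects for analysis". 200 × (1 − 0.15) = 170, so this reproduces (85 per arm at 1:1). The statement of "at least 90% power to detect at a 0.05 significance level" cannot be checked, because the SD, correlation and Table 3 effects are not in the text available. Below, two-sided 0.05 is assumed, A1C is in SD units, and the correlation r is an assumption, shown over 0.5–0.8.

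**Step 1: the model read literally.** With baseline as an outcome and a free group term, complete data make the 3-month contrast a difference in mean change. Its variance is proportional to 2(1 − r). Under compound symmetry the covariance of an earlier A1C with change is r − r = 0, so adding it removes nothing. An exact generalised least squares calculation with 85 per arm agrees: the variance stays at 0.02353 (r = 0.5) and 0.00941 (r = 0.8), whether the earlier value enters as a main effect or by visit. If the correlation between the earlier and 3-month values is a lower s, the cancellation is not exact but little is gained: (s − r)²/[2(1 − r)] = 0.01/0.4 = 2.5% at r = 0.8, s = 0.70.

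**Step 2: condition on Visit 1.** The variance becomes 1 − r². Relative to step 1 the cut is 1 − (1 − r²)/[2(1 − r)] = (1 − r)/2, which is 25% at r = 0.5 and 10% at r = 0.8.

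**Step 3: add the earlier value under compound symmetry.** The variance becomes 1 − 2r²/(1 + r). The ratio to step 2 is (1 + 2r)/(1 + r)², a further cut of r²/(1 + r)².

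| r | Step 2 | Step 3 | Ratio | Further cut | 170 ÷ ratio |
|---|---|---|---|---|---|
| 0.5 | 0.750 | 0.667 | 0.889 | 11.1% | 191 |
| 0.7 | 0.510 | 0.424 | 0.830 | 17.0% | 205 |
| 0.8 | 0.360 | 0.289 | 0.802 | 19.8% | 212 |

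Take an effect with 90% power at step 2. Power at step 3 is Φ(3.2415/√ratio − 1.96), which is 93.0%, 94.5% and 95.1% for the three rows. The difference detectable at 90% power, 3.2415 × √(2/85) × √variance, falls from 0.431 to 0.406 SD (r = 0.5) and from 0.298 to 0.267 SD (r = 0.8). Steps 2 and 3 together cut the step 1 variance by 33% (1 − 0.667/1.0) and 28% (1 − 0.289/0.4).

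**Step 4: let the correlation decay.** With adjacent correlation r and earlier-to-3-month correlation s, the further cut is (s − r²)²/(1 − r²)².
- r = 0.8, s = 0.75: (0.11/0.36)² = 9.3%
- r = 0.7, s = 0.65: (0.16/0.51)² = 9.8%
- r = 0.5, s = 0.40: (0.15/0.75)² = 4.0%
- r = 0.8, s = 0.70: (0.06/0.36)² = 2.8%
- first-order autoregression, s = r²: 0%

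**Step 5: incomplete availability.** Scaling the step 3 ceiling roughly by the share of teens with a value gives 9–16% at 80% availability (0.8 × 11.1% and 0.8 × 19.8%) and 6–10% at 50%, before any decay.

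**The case against.** One baseline with a mixed model is a standard design, and nothing in 9.3.1 is contradictory or invalid. A reader might infer three stronger things, none of which the documents support.

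- *That adding the earlier A1C to 9.3.1 as it stands yields 11–20%.* Step 1 shows no gain there under the plan's own covariance assumption. The benefit depends wholly on conditioning on Visit 1. At r = 0.5 that step is the larger gain (25% against 11%); at r = 0.8 it is the smaller (10% against 20%).
- *That 11–20% is the expected gain.* It is a ceiling. The documents available give no r, and 9.3.1 treats compound symmetry as provisional. A 12-month look-back would put the earlier value up to 15 months before the 3-month one. Section 4.2 notes that control often worsens at this age. A shared drift would not matter, but differences between teens in that drift would lower the correlation. Section 5.3 also allows a home A1C kit at follow-up, so methods may differ.
- *That every teen has an earlier value on record.* Twelve months since diagnosis is not twelve months at this clinic. The summary of changes reports missing point-of-care A1C during telehealth, and 5.3 adds outside recruitment channels. The logged consent change "to be able to collect clinical data (A1C) from participants that consent to screen for the study" concerns teens who do not enrol, so it is not authority to abstract historical values from those who do.

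All of this limits the size of the gain. It does not remove the point: once Visit 1 is conditioned on, a pre-randomisation covariate introduces no bias. If the value proves uninformative, the loss is about one degree of freedom per fitted term. With the value and a missing indicator at each visit, that is roughly 2/170, or about 1% in variance.

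**Conclusion.** The point holds as a cheap improvement. The plan leaves precision unused in two linked ways: 9.3.1 does not specify how the Visit 1 A1C is conditioned on, and no earlier A1C is used. Given conditioning on Visit 1, the earlier value reduces the variance of the 3-month contrast by at most 11–20%. That ceiling assumes r of 0.5–0.8, compound symmetry and a value for everyone. About 3–10% is more plausible with decaying correlation, less with incomplete availability, and zero under first-order autoregression. Availability is inferred from the 12-month criterion and clinic-based recruitment, not documented. This is a missed efficiency gain. It is not an error or a source of bias, and it is no evidence that the trial falls short of its stated power.

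**What to change.** In 9.3.1:

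1. State how the model conditions on the Visit 1 A1C. Either model the 3-, 6- and 12-month A1C with Visit 1 A1C by visit as a covariate, or keep baseline as an outcome and constrain its mean to be equal across arms. The covariate form excludes nobody further, because 9.3.1 already requires a baseline and at least one follow-up value.
2. Add the most recent clinic A1C before enrolment as a pre-specified covariate by visit, for example from the 12 months before Visit 1. Where there is none, use mean imputation with a missing indicator. This is acceptable for a pre-randomisation covariate and keeps everyone in the analysis.

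In 1.3 and section 3, add this value and its date to the baseline clinical data. Specify the change before any unblinded analysis, and abstract the values without reference to arm.

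The cost is abstracting one existing value for up to 200 teens, one or two sentences of analysis wording, and possibly added authorisation for families already enrolled. Some values will be missing. No new visit or test is needed. Step 1 is worth doing even if step 2 is not; step 2 should not be adopted without step 1.

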## 4 STUDY DESIGN

### 4.1 OVERALL DESIGN

To test the effects of the proposed intervention, we will recruit a sample of 200 adolescents with T1D and their parents from two clinical sites (Vanderbilt University Medical Center and Children's National Medical Center, 100 dyads from each site). Adolescents will be eligible if they (1) are between the ages of 13-17; (2) have been diagnosed with T1D for at least 12 months; (3) score above the clinical cutoff on a screening tool for diabetes distress; and (4) speak and read English. The sampling goal for this study across the two sites is 68% white, 10% Hispanic, 16% Black, and 6% Asian, with equal numbers of boys and girls, in line with recent studies conducted in these settings.

If the adolescent is eligible, the RA will obtain informed consent/assent, and the adolescent and his/her parent will complete the baseline measures. Participants will then be randomly assigned to one of two conditions: Positive Affect and Education (n=100) or Education only (n=100). Randomization will be stratified by use of diabetes devices (insulin pump and CGM), to avoiding confounding effects. A computer program will generate the randomization scheme.

After completing the exit interview, participants who use/have used a continuous glucose monitor (CGM) will be offered the opportunity to participate in a secondary study to discuss the role of CGM in their diabetes management.

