### 5.3 STRATEGIES FOR RECRUITMENT AND RETENTION

Enrollment. We will recruit a sample of 200 adolescents with T1D and their parents from two clinical sites (Vanderbilt University Medical Center and Children's National Medical Center), 100 from each site. The sampling goal for this study across the two sites is 68% white, 10% Hispanic, 16% Black, and 6% Asian, with equal numbers of boys and girls, in line with recent studies conducted in these settings. We will employ a method of enrolling subjects that has been evaluated and refined as part of our prior work.

At CNMC, there are currently **614 active patients** with T1D between the ages of 13-17 years, and there are no current competing studies within this age group. The adolescent patient population is 47% female and 52% Caucasian. Thus, CNMC is well-positioned to provide an adequate and diverse sampling of participants for the proposed study.

At VUMC, there are currently **1100 active patients** between the ages of 13-17, and the adolescent patient population is 48% female and 75% Caucasian. Thus, we do not anticipate difficulty in meeting our enrollment goals.

We created recruitment videos to explain the study in a brief and engaging format:

<https://youtu.be/IQT4REruoQ> (VUMC); [https://youtu.be/Uinw\\_a8\\_5Lo](https://youtu.be/Uinw_a8_5Lo) (CNH)

We will also use Research Match and the Vanderbilt Research Notifications Distribution list to reach more potential VUMC participants.

After completing visit 2 (3 month follow up data collection and exit interview) we will invite 20 youth participants who currently use/have used a CGM to participate in an optional interview to describe the role of CGM on their diabetes management.

Screening. We will screen adolescents for diabetes distress using a validated measure, the Problem Areas in Diabetes-Teens scale (PAID-T). In order to meet our enrollment goals, enrolling 4-5 per month per site, we will plan to screen 10-12 families per week.

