### 6.3 MEASURES TO MINIMIZE BIAS: RANDOMIZATION AND BLINDING

The randomization scheme will be determined by the biostatistician, and adolescents will be stratified by diabetes device use (insulin pumps, continuous glucose monitors).

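### Site is neither a named stratification factor nor a model term in this two-clinic trial; the likely effect on the A1C result is small, and prespecifying site and site-by-visit in 9.3.1 is a cheap improvement

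*Combined protocol and SAP*

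**What the plan says.** **Sample.** Section 4.1 plans "100 dyads from each site" and two arms: "Positive Affect and Education (n=100) or Education only (n=100").

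**Randomisation.** Section 4.1: "Randomization will be stratified by use of diabetes devices (insulin pump and CGM), to avoiding confounding effects". Section 6.3: "adolescents will be stratified by diabetes device use (insulin pumps, continuous glucose monitors"). Neither mentions site. Section 9.3.1 refers in passing to a randomised block design, without giving the block factor or block size.

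**Model.** Section 9.3.1: "we will use time, treatment group and the interaction of treatment with time serving as the main explanatory variables". It adds a subject-level random intercept and says "we will adjust for age, sex, and race/ethnicity to improve precision". Adjusted and unadjusted treatment estimates will be compared. Site does not appear in the hypotheses (9.1), the main model (9.3.1) or the moderators (9.3.2).

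**The two clinics.** Section 5.3 says of Children's National: "The adolescent patient population is 47% female and 52% Caucasian". Of Vanderbilt it says: "the adolescent patient population is 48% female and 75% Caucasian". It also describes two extra recruitment channels aimed at Vanderbilt participants only.

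**The concern.** Section 4.1 gives the avoidance of confounding as the reason for stratifying. Site is the largest planned split of the sample, half and half, yet it is left to chance in the allocation and is absent from the analysis. If A1C changed differently at the two clinics over follow-up, that difference would add to residual variance. In the one trial actually run, it could also fall unevenly on the arms. Readers of a two-site trial will ask about this, and the plan gives no prespecified answer.

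**Working it through.** **1. The plan's own figure.** Section 9.2: 200 × (1 − 0.15) = 170 for analysis, which reproduces. The 90% power claim cannot be checked, because the table of effect sizes is not in the text available.

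**2. Chance imbalance in site mix.** Inputs from 4.1: 200 dyads, 100 per site, 100 per arm. If allocation ignores site, the number X from one site in one arm is hypergeometric(200, 100, 100).

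- SD(X) = √[100 × 0.5 × 0.5 × (200 − 100)/(200 − 1)] = √12.56 = 3.54.
- The between-arm difference in site share is (2X − 100)/100, so its SD is 2 × 3.54 = 7.1 percentage points.

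| Split (one arm / other arm) | Difference in site share | Probability of this or worse |
|---|---|---|
| 55 / 45 | 10 points | 20.3% |
| 57 / 43 | 14 points | 6.6% |
| 60 / 40 | 20 points | 0.7% |

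A simulation with permuted blocks of 4 inside four device strata pooled over sites (block size and device mix assumed) gave 16–19%, 5–6% and about 0.5%. Device stratification does not control site.

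**3. What the documented difference amounts to.** The racial-mix gap is 75 − 52 = 23 percentage points. If the enrolled samples mirror the clinic populations, a 10-point site imbalance carries 0.10 × 23 = 2.3 points of racial imbalance between arms. Sex is nearly equal (47% v 48% female).

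**4. Which site differences reach the treatment contrast.** Suppose one site reads higher by a constant s at every visit. A subject's change is (y₃ + s) − (y₀ + s) = y₃ − y₀, and s drops out. The 9.3.1 model includes the baseline measurement and tests treatment-by-time, so a stable offset cancels with complete data and largely cancels otherwise. Only a site difference in change, δ, remains.

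**5. Size of the shift.** Shift = δ × imbalance. The documents give no A1C by site, so δ is assumed.

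| Assumed δ (A1C points) | 10-point imbalance | 20-point imbalance |
|---|---|---|
| 0.1 | 0.01 | 0.02 |
| 0.3 | 0.03 | 0.06 |
| 0.5 | 0.05 | 0.10 |

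The mean absolute imbalance is about 7.09 × √(2/π) = 5.7 points, so at δ = 0.3 the typical shift is 0.3 × 0.057 = 0.017.

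**6. Scale.** Assume the SD of A1C change is 1.0 to 1.5 (not in the documents). With 85 per arm, the standard error is SD × √(2/85) = 0.153 to 0.230. A 0.03 shift is 0.03/0.230 = 13% to 0.03/0.153 = 20% of one standard error. The share of variance due to site is δ²/4 = 0.0225, or 0.0225/2.25 = 1.0% to 0.0225/1.0 = 2.3%.

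**7. Cost of adjusting.** Site (1) plus site by four visits (3) = 4 degrees of freedom, with about 170 subjects analysed.

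**The case against.** The case for leaving the plan alone has real force.

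- **No bias on average.** Imbalance under randomisation is random and already reflected in the standard error. This stands: a reader might infer that site confounds the trial, and the documents do not support that.
- **Few documented site differences.** A reader might also infer that the clinics are known to differ in interview staff, usual care or A1C testing. Section 6.2.1 says only that trained staff deliver the contract and interview, and no section describes A1C equipment by site. Such differences are plausible but undocumented. Clinic size (614 v 1100 patients) describes the recruitment pool and is not shown to be prognostic.
- **Race/ethnicity is already a covariate.** This stands for the adjusted model and covers the one material difference in population mix. It does not help the unadjusted model, and it does not stand in for care, staff or recruitment route.
- **A stable measurement offset cancels.** This largely stands (step 4). The home A1C kit in 5.3 could make an offset less stable if uptake differed by site, but the documents do not say that it did.
- **The blocks may be kept by site.** Section 9.3.1 does not rule this out, and no section states it. If they are, the allocation half of the point is answered; the model would then omit a factor used in the randomisation.
- **Changing the list is not free.** The summary of changes runs from October 2019 to August 2021, during recruitment. Re-stratifying midway leaves two schemes and some incomplete blocks. For that reason the model change comes first.

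**Conclusion.** The point holds as a modest one. Site is balanced by no stated rule and adjusted for in no model. Without site stratification there is about a one-in-five chance of a 10-point or larger difference in site mix between arms. The likely consequence is small: about 0.02 to 0.03 A1C points for an assumed 0.3-point site difference in A1C change, with about 1–2% of variance attributable to site if the SD of change is 1.0 to 1.5. The imbalance probability rests on the planned 100/100 split by site and by arm, and on lists not being kept by site. The A1C figures rest on assumptions, because no site-specific A1C is given. Nothing here suggests that the trial's conclusion is biased or that the sample size must change. The case for acting is that the analysis change costs very little and settles the question in advance.

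**What to change.** **Analysis (main change), 9.3.1.** Prespecify site and site-by-visit as fixed effects in the primary A1C model and in each secondary model, before outcome data by arm are seen. Report the number randomised and analysed by site and arm. The site-by-visit term is the one that removes site differences in change; a site main effect alone would deal only with level.

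**Randomisation (secondary), 4.1 and 6.3.** Define the blocks and state whether lists are kept separately by site. If they are not and randomisation is still open, stratify by site as well as device use, where the list can be changed without disruption.

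**Cost.** Analysis-plan wording and about four degrees of freedom; no new participants, visits or data. If re-stratified, two sites by four pump/CGM combinations give 8 cells for 200 dyads, an average of 25 each, with some smaller cells and incomplete blocks.
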